APPENDIX 4. VITAL SIGNS MEASUREMENTS

Vital Sign parameter		Grading Scale	Gradable with Toxicity Grading Scale for Healthy Adult and Adolescent Preventive Vaccine Clinical Study Gradable with Common Terminology Criteria for Adverse Events (CTCAE)			
			Markedly Abnormal			Grade 4
			Grade 1	Grade 2	Grade 3	
Temperature (°C), considering that °C = (°F - 32) / 1,8		a	>=38.0 – <38.5 °C >=100.4 – <101.1 °F	>=38.5 – <39 °C >=101.1 – <102.0 °F	>=39.0 – <40 °C >=102.0 – <104 °F	>= 40 °C >= 104 °F
Respiratory Rate (resp/min)		a	>=17 – <20	>=20 – <25	>= 25	Intubation
Weight (kg)	Weight gain	b	>=5 - <10% from baseline	>=10 - <20% from baseline	>=20% from baseline	NA
	Weight loss	b	>=5 to <10% from baseline; intervention not indicated	>=10 to <20% from baseline; nutritional support indicated	>=20% from baseline; tube feeding or total parenteral nutrition (TPN) indicated	NA
Heart Rate (bpm)	Tachycardia	a	>=101 – <115	>=115 – <130	>= 130	Emergency visit or hos for arrhyth
	Bradycardia	a	>50 – <=55	>45 – <=50	<= 45	Emergency visit or hos for arrhyth
Systolic Blood Pressure (mmHg)	Hypertension	a	>=141 – <150	>=150 – <155	>= 155	Emergency visit or hos for maligna hypertensi

Document: K:\AAA\Ga-PSMA-R2\VYA27826\Biostatistics\Documentation\SAP\v2.0\Ga-PSMA-R2-SAP_...
 Author: 

Template No.: CS_TP_BS016 Revision 5
 Effective Date: 01Apr2018

 Statistical Analysis Plan

Vital Sign parameter		Grading Scale	Gradable with Toxicity Grading Scale for Healthy Adult and Adolescent Preventive Vaccine Clinical Study Gradable with Common Terminology Criteria for Adverse Events (CTCAE)			
			Markedly Abnormal			Grade 4
			Grade 1	Grade 2	Grade 3	
	Hypotension	a	>85 – <=89	>80 – <=85	<= 80	Emergency visit or hospitalization for hypotension
Diastolic Blood Pressure (mmHg)	Hypertension	a	>=91 – <95	>=95 – <100	>= 100	Emergency visit or hospitalization for malignant hypertension

[figure not shown]
Document: K:\AAA\Ga-PSMA-R2\VYA27826\Biostatistics\Documentation\SAP\v2.0\Ga-PSMA-R2-SAP_ \

Author:  \

Template No.: CS_TP_BS016 Revision 5 F

Effective Date: 01Apr2018

Statistical Analysis Plan

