Illness or clinical adverse event (as defined according to applicable regulations)	No interference with activity	Some interference with activity not requiring medical intervention	Prevents daily activity and requires medical intervention	ER visit or hospitalization

B. Tables for Laboratory Abnormalities

The laboratory values provided in the tables below serve as guidelines and are dependent upon institutional normal parameters. Institutional normal reference ranges should be provided to demonstrate that they are appropriate.

Serum *	Mild (Grade 1)	Moderate (Grade 2)	Severe (Grade 3)	Potentially Life Threatening (Grade 4)**
Sodium – Hyponatremia mEq/L	132 - 134	130 - 131	125 - 129	<125
Sodium – Hypernatremia mEq/L	144 - 145	146 - 147	148-150	>150
Potassium – Hyperkalemia mEq/L	5.1 - 5.2	5.3 - 5.4	5.5 - 5.6	> 5.6
Potassium – Hypokalemia mEq/L	3.5 - 3.6	3.3 - 3.4	3.1 - 3.2	< 3.1
Glucose – Hypoglycemia mg/dL	65 - 69	55-64	45 - 54	< 45
Glucose – Hyperglycemia Fasting – mg/dL Random – mg/dL	100 – 110 110 – 125	111 – 125 126 – 200	>125 >200	Insulin requirements or hyperosmolar coma
Blood Urea Nitrogen BUN mg/dL	23 - 26	27 – 31	> 31	Requires dialysis
Creatinine – mg/dL	1.5 – 1.7	1.8 - 2.0	2.1 – 2.5	> 2.5 or requires dialysis
Calcium – hypocalcemia mg/dL	8.0 - 8.4	7.5 – 7.9	7.0 - 7.4	< 7.0
Calcium – hypercalcemia mg/dL	10.5 - 11.0	11.1 - 11.5	11.6 - 12.0	> 12.0
Magnesium – hypomagnesemia mg/dL	1.3 – 1.5	1.1 – 1.2	0.9 – 1.0	< 0.9
Phosphorous – hypophosphatemia mg/dL	2.3 – 2.5	2.0-2.2	1.6 – 1.9	< 1.6
CPK – mg/dL	1.25 – 1.5 x ULN***	1.6 – 3.0 x ULN	3.1 –10 x ULN	> 10 x ULN
Albumin – Hypoalbuminemia g/dL	2.8 - 3.1	2.5 – 2.7	< 2.5	
Total Protein – Hypoproteinemia g/dL	5.5-6.0	5.0 - 5.4	< 5.0	
Alkaline phosphate – increase by factor	1.1 – 2.0 x ULN	2.1 – 3.0 x ULN	. 3.1 – 10 x ULN	$> 10 \mathrm{x} \mathrm{ULN}$
Liver Function Tests –ALT, AST increase by factor	1.1 – 2.5 x ULN	2.6 – 5.0 x ULN	5.1 – 10 x ULN	> 10 x ULN
Bilirubin – when accompanied by any increase in Liver Function Test increase by factor	1.1 – 1.25 x ULN	1.26 – 1.5 x ULN	1.51 – 1.75 x ULN	> 1.75 x ULN
Bilirubin – when Liver Function Test is normal; increase by factor	1.1 – 1.5 x ULN	1.6 – 2.0 x ULN	2.0 – 3.0 x ULN	> 3.0 x ULN
Cholesterol	201 - 210	211 - 225	> 226	
Pancreatic enzymes _ amylase linase	$11 - 15 \times 11$ N	$16 - 20 \times III N$	$21 - 50 \times III N$	$> 5.0 \times III N$

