14.2. LABORATORY EVALUATIONS

Results from the local laboratory will be included in the reporting of this study for Hematology, Blood Chemistry and Urinalysis. A list of laboratory assessments to be included in the outputs, and a severity grading system is included in APPENDIX 3.

Presentations will use SI Units.

Quantitative laboratory measurements reported as "< X", i.e. below the lower limit of quantification (BLQ), or "> X", i.e. above the upper limit of quantification (ULQ), will be converted to X for the purpose of quantitative summaries, but will be presented as recorded, i.e. as "< X" or "> X" in the listings.

The following summaries will be provided for laboratory data:

- Observed values and change from baseline by visit (for quantitative measurements)
- Summary of qualitative clinical laboratory evaluations by visit
- Incidence of abnormal values at any time post-baseline according to normal range criteria
- Shift from baseline according to normal range criteria (for quantitative measurements and categorical measurements), by visit
- Shift from baseline to worst post-baseline value, according to severity grading system
- Summary of markedly abnormal post-baseline values
- Listing of patients with Grade 3 or above severity grades
- Box plots of absolute values over time and changes from baseline over time

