eGFR (Any eGFR value > 90 will be classified as Grade 0)		b	$\leq 90 - > 60 \text{ ml/min/1.73 m}^2$	$\leq 60 - > 30 \text{ ml/min/1.73 m}^2$	$\leq 30 - > 15 \text{ ml/min/1.73 m}^2$	$\leq 15 \text{ ml/min/1.73 m}^2$
LDH		d	NA	NA	NA	NA

Document: K:\AAA\Ga-PSMA-R2\VYA27826\Biostatistics\Documentation\SAP\v2.0\Ga-PSMA-R2-SAP
 Author: [Redacted]

Template No.: CS_TP_BS016 Revision 5
 Effective Date: 01Apr2018

Statistical Analysis Plan

Laboratory parameter		Grading Scale	a) Gradable with Toxicity Grading Scale for Healthy Adult and Adolescent Volunteers Enrolled in Preventive Vaccine Clinical Study b) Gradable with Common Terminology Criteria for Adverse Events Version 4.03 c) Gradable with University of Delaware Criteria (http://www1.udel.edu/mls/mclane/KMS3RR.html) d) Not Gradable				
			Grade 1	Grade 2	Grade 3	Markedly Abnormal	
Corrected Calcium	Hypercalcemia	a	>=2.625 - <2.75 mmol/L	>=2.75 - <2.875 mmol/L	>=2.875 - <3 mmol/L	>= 3 mmol/L	
	Hypocalcemia	a	>=2 - <2.1 mmol/L	>=1.875 - <2 mmol/L	>=1.75 - <1.875 mmol/L	<1.75 mmol/L	
Serum creatinine		a	>=132.6 - < 150.28 umol/L	>=150.28 - <176.8 umol/L	>=176.8 - <221 umol/L	>= 221 umol/L requires recheck	
Sodium	Hypernatremia	a	>=144 - <145 mmol/L	>=145 - <147 mmol/L	>=147 - <150 mmol/L	>=150 mmol/L	
	Hyponatremia	a	>=132 - <134 mmol/L	>=130 - <132 mmol/L	>=125 - <130 mmol/L	<125 mmol/L	
Potassium	Hyperkalemia	a	>=5.1 - <5.2 mmol/L	>=5.2 - <5.4 mmol/L	>=5.4 - <5.6 mmol/L	>= 5.6 mmol/L	
	Hypokalemia	a	>=3.5 - <3.6 mmol/L	>=3.3 - <3.5 mmol/L	>=3.1 - <3.3 mmol/L	< 3.1 mmol/L	
Uric acid		b	>ULN - 10 mg/dL (0.59 mmol/L) without physiologic consequences	NA	>ULN - 10 mg/dL (0.59 mmol/L) with physiologic consequences	>10 mg mmol/L	
Chloride		d	NA	NA	NA	NA	
Hematology							
RBC		d	NA	NA	NA	NA	
White blood cells with differential	WBC	Increased	a	>=10.8 - <15 10 ⁹ /L	>=15 - <20 10 ⁹ /L	>=20 - <25 10 ⁹ /L	>= 25 10 ⁹ /L
		Decreased	a	>2.5 - <=3.5 10 ⁹ /L	>1.5 - <=2.5 10 ⁹ /L	>1 - <=1.5 10 ⁹ /L	<= 1 10 ⁹ /L
	Monocytes		d	NA	NA	NA	NA
	Eosinophils		a	>=0.65 - <1.5 10 ⁹ /L	>=1.5 - <5 10 ⁹ /L	>=5 10 ⁹ /L	Hyperleukocytosis

Document: K:\AAA\Ga-PSMA-R2\VYA27826\Biostatistics\Documentation\SAP\v2.0\Ga-PSMA-R2-SAP_...
 Author: [Redacted]

Template No.: CS_TP_BS016 Revision 5
 Effective Date: 01Apr2018

Statistical Analysis Plan

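### SAP Appendices 3 and 4 cite the protocol 11.2 toxicity scale but do not reproduce its limits, so values at band edges are mostly graded one step too high and a few too low

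*SAP*

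**What the plan says.** Protocol 11.2 sets out a toxicity scale in closed bands, and Protocol 7.1 has adverse events recorded on it. SAP 14.2.2 names the same scale as one of three sources for laboratory grading. Appendices 3 and 4 mark with code a the rows that use it.

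Those rows are rewritten as half-open intervals:

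- **High potassium.** In the protocol row "Potassium – Hyperkalemia mEq/L", Grades 1 to 3 are 5.1–5.2, 5.3–5.4 and 5.5–5.6, with Grade 4 above 5.6. The SAP's Grade 2 is ">=5.2 - <5.4 mmol/L".
- **High sodium.** Protocol Grades 1 and 2 are 144–145 and 146–147. The SAP's Grade 2 is ">=145 - <147 mmol/L".
- **Low sodium.** Protocol Grade 1 is 132–134. The SAP's Grade 1 is ">=132 - <134 mmol/L".
- **Temperature.** The SAP's Grade 2 is ">=38.5 – <39 °C >=101.1 – <102.0 °F" and its Grade 3 is ">=39.0 – <40 °C >=102.0 – <104 °F". The row label gives the conversion: "considering that °C = (°F - 32) / 1,8".

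SAP 14.2 uses the laboratory grades in a shift to the worst post-baseline grade, a summary of markedly abnormal values and a "Listing of patients with Grade 3 or above severity grades". SAP 14.4 plans an incidence, a shift and a listing of markedly abnormal vital signs, and points to Appendix 4 for the grading.

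**The concern.** If two documents grade by the same named scale, a given value should get the same grade in both. Here the last value of a protocol band is often the first value of the SAP's next grade. Many of these are plausible recorded readings, such as diastolic pressure 100 or platelets 100. A programmer who follows the SAP exactly will produce grade tables that differ from the scale the report says it used.

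Safety is the primary objective, and the Grade 3 boundary decides who appears in the laboratory listing. Where an abnormal value is also reported as an adverse event, the investigator grades it on Protocol 11.2 and the laboratory table grades it on Appendix 3. One value can then carry two grades in one report.

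**Working it through.** **1. The SAP's own temperature pairs.** With °C = (°F − 32)/1.8, so °F = 1.8 × °C + 32:

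- 38.0 °C: 68.4 + 32 = 100.4 °F, as printed.
- 38.5 °C: 69.3 + 32 = 101.3 °F; the SAP prints 101.1.
- 39.0 °C: 70.2 + 32 = 102.2 °F; the SAP prints 102.0.
- 40 °C: 72 + 32 = 104 °F, as printed.

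In the other direction, 101.1 °F is 69.1/1.8 = 38.39 °C, which is Grade 1 by °C and Grade 2 by °F. 102.0 °F is 70.0/1.8 = 38.89 °C, which is Grade 2 by °C and Grade 3 by °F.

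**2. Edge values, protocol against SAP.** Every value on a reporting grid (whole units or one decimal; 0.01 for lymphocytes and neutrophils) was graded by both tables. Laboratory limits were compared in protocol units, using the factors implied by the SAP's SI limits. For creatinine the factor is 132.6/1.5 = 88.4, so the SAP's 176.8 µmol/L is 2.0 mg/dL. Examples:

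| Value | Protocol 11.2 | SAP |
|---|---|---|
| Respiratory rate 25 | 2 | 3 |
| Heart rate 130; 45 | 2 | 3 |
| Systolic BP 155; 80 | 2 | 3 |
| Diastolic BP 100 | 2 | 3 |
| Sodium 147 | 2 | 3 |
| Potassium 5.4 | 2 | 3 |
| Creatinine 2.0 mg/dL | 2 | 3 |
| Hb 10.5 | 2 | 3 |
| Platelets 100 | 2 | 3 |
| Hb 8.5 | 3 | 4 |
| Platelets 25 | 3 | 4 |
| Sodium 134 | 1 | ungraded |
| Potassium 3.6 | 1 | ungraded |
| Calcium 8.4 mg/dL | 1 | ungraded |
| Glucose 69 mg/dL | 1 | ungraded |

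Appendix 4 has 17 mismatches, all one grade high. Three of them are the °F values 101.1, 102.0 and 104, so 17 − 3 = 14 remain if temperature is graded in °C, where only 40.0 shifts. Appendix 3 has 43 values one grade high and 6 one grade low. The total is 17 + 43 = 60 high and 6 low. The count treats ALT and AST as one row and leaves out bilirubin, eosinophils and the row for hemoglobin change.

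**3. BUN.** The SAP limits imply two factors: 8.211/23 = 0.357, but 9.75/26 = 11.625/31 = 0.375. If the data are converted with 0.357:

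- BUN 27 becomes 27 × 0.357 = 9.639, below 9.75, so Grade 1 instead of the protocol's Grade 2.
- BUN 32 becomes 32 × 0.357 = 11.424, below 11.625, so Grade 2 instead of Grade 3.

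**4. Bilirubin.** With raised liver tests the protocol's Grade 4 starts above 1.75 × ULN; the SAP gives that limit to normal liver tests. At 1.8 × ULN with raised tests the grade is 4 in the protocol and 2 in the SAP. With normal tests it is 2 in the protocol and 4 in the SAP.

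**5. Weight of one patient.** 1/30 = 3.3 percentage points overall, 1/12 = 8.3 in a Phase 2 group and 1/6 = 16.7 in the Phase 1 group, which SAP 6.1 presents separately.

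**The case against.** The best defense is that the protocol's bands leave gaps. A creatinine between 1.7 and 1.8 mg/dL, or an ALT between 2.5 and 2.6 × ULN, has no printed grade, so the SAP needed a rule. Protocol 11.2 also calls its laboratory limits guidelines that depend on institutional ranges. The need for a gap rule stands. It does not justify regrading values the scale prints: heart rate, respiratory rate and blood pressure in whole units have no gaps between grades to close. Nor is the shift a consistent convention. The low-sodium and low-potassium rows keep the protocol's lower limits for Grades 2 and 3, while the hemoglobin, platelet and low-WBC rows move them. The guidelines wording does not explain fixed limits that differ under the same label.

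A reader might infer four stronger things that the documents do not support:

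- **That temperatures will be misgraded in the tables.** SAP 14.4 reports temperature in °C after conversion, and 38.5 and 39.0 °C agree with the protocol. The protocol's own scale has a similar rounding mismatch at 101.2 and 102.1 °F (38.44 and 38.94 °C).
- **That every edge value is graded too high.** Six go down.
- **That the primary safety analysis as a whole is affected.** AE severity tables use reported severity (SAP 14.1.1.1), and the change-from-baseline and normal-range outputs do not use these grades. The worst-grade shift and Grade 3+ listing are planned for laboratory data only.
- **That a known share of readings is affected.** The documents give no distribution of values, so no frequency can be stated.

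**Conclusion.** The point holds as a mismatch between the SAP appendices and the scale they cite. Printed edge values are mostly graded one step too high, and many of them cross from Grade 2 to Grade 3. A few fall one step. The bilirubin exchange is larger, at two grades in the 1.8 × ULN example.

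The consequence is limited to descriptive outputs: the three grade-based laboratory displays in SAP 14.2 and the markedly abnormal vital-sign displays in SAP 14.4. No formal testing is planned (SAP 6.6), so no inference changes. With about 30 patients, though, a single reclassification is visible. It should be corrected before lock.

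This rests on three assumptions: values are recorded in the protocol's units and precision or convert with the implied factors; BUN data are converted with 0.357; and the markedly abnormal label covers Grade 3 and above, since the table header does not make its span clear. If the label covers only Grade 4, fewer of the vital-sign shifts matter. The temperature conflict is secondary and has effect only if the °F limits are programmed.

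**What to change.** Before database lock:

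1. Reconcile every row coded a in Appendices 3 and 4 with Protocol 11.2, so that each value printed there keeps its printed grade. Include the end values of the low-side Grade 1 bands (sodium 134, potassium 3.6, calcium 8.4 and glucose 69 mg/dL).
2. Use one conversion factor per analyte, and state it. BUN needs this first.
3. State one rule for values that fall in the gaps between printed bands, and apply it to all rows.
4. Grade temperature on converted °C and delete the °F limits.
5. Reconcile the two bilirubin rows with the protocol in the same row-by-row check, together with the rows left out of the count above.

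The cost is a correction to two SAP appendices and the matching grading formats. No new data are needed.

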APPENDIX 5. DOSIMETRY MEASUREMENTS

TEST	Organs / Lesions
Decay corrected tissue activity	Brain
	Heart Wall
	Kidneys
	Lacrimal Glands
	Liver
	Lungs
	Red Marrow
	Salivary Glands
	Spleen
	Thyroid
	Urinary Bladder
	Lesion 1
	...
	Lesion 10
Percent GI excretion	
Non-decay corrected tissue activity	Brain
	Heart Wall
	Kidneys
	Lacrimal Glands
	Liver
	Lungs
	Red Marrow
	Salivary Glands
	Spleen
	Thyroid
	Urinary Bladder
	Lesion 1
	...
	Lesion 10
Absorbed doses	Brain

[figure not shown]
Document: K:\AAA\Ga-PSMA-R2\VYA27826\Biostatistics\Documentation\SAP\v2.0\Ga-PSMA-R2-SAP_ \

Author: [Redacted] \

Template No.: CS_TP_BS016 Revision 5 F

Effective Date: 01Apr2018

Statistical Analysis Plan

	Heart
	Kidneys
	Lacrimal glands
	Liver
	Lungs
	Red Marrow
	Salivary glands
	Spleen
	Urinary Bladder
Whole body dose	
Effective dose	
Lesion doses	Lesion 1
	...
	Lesion 10
Residence times	Brain
	Heart
	Kidneys
	Lacrimal glands
	Liver
	Lungs
	Red marrow
	Salivary glands
	Spleen
	Thyroid
	Urinary bladder
	Remainder
	Lesion 1
	...
	Lesion 10

Document: K:\AAA\Ga-PSMA-R2\VYA27826\Biostatistics\Documentation\SAP\v2.0\Ga-PSMA-R2-SAP_ \

Author: [Redacted] \

Template No.: CS_TP_BS016 Revision 5 F

Effective Date: 01Apr2018

Statistical Analysis Plan - V2.0 - 30-Jun-2020

Electronic Signature Manifestation

This page is a manifestation of the electronic signature(s) used in compliance with the organization's electronic signature policies and procedures.

Signer Full Name	Meaning of Signature	Date and Time
██████████	Document Approval (I certify that I have the education, training and experience to perform this task)	29 Jun 2020 18:41:56 UTC
██████████	Document Approval (I certify that I have the education, training and experience to perform this task)	29 Jun 2020 21:10:52 UTC
██████████	Document Approval (I certify that I have the education, training and experience to perform this task)	29 Jun 2020 22:07:59 UTC
██████████	Document Approval (I certify that I have the education, training and experience to perform this task)	30 Jun 2020 11:14:30 UTC

Official Title: A Phase 1/2 open-label, multi-center, safety and tolerability study of a single dose of ⁶⁸Ga-PSMA-R2 in patients with biochemical relapse (BR) and metastatic prostate cancer (mPCa)

NCT Number: NCT03490032

Document Date: SAP Amendment 1: 03 August 2018

**STATISTICAL ANALYSIS PLAN AMENDMENT 1
PK ANALYSIS**

**Advanced Accelerator Applications International SA Study Number: A206D-A01-001
Protocol Version: Version 2.2

1. INTRODUCTION

This statistical analysis plan (SAP) describes the statistical methods to be used during the reporting of pharmacokinetic (PK) data collected under Advanced Accelerator Applications International SA (AAA) protocol Number: A206D-A01-001.

This SAP should be read in conjunction with the study protocol and all applicable Statistical Analysis Plans and/or Workplans for the study. This version of the plan has been developed using the protocol document Version 2.2 dated 22 February 2018. Any further changes to the protocol may require updates to the SAP. Any deviation from this analysis plan will be described in detail in the clinical report. An overall final report of pharmacokinetic data will be prepared and provided by [REDACTED].

2. OBJECTIVES

The objectives of this study are as follows:

Primary Objective:

- To assess safety and tolerability of a single administration of 3 mega Becquerel (MBq)/kg, but not less than 150 MBq and not more than 250 MBq, of ⁶⁸Ga-PSMA-R2.

Secondary Objective:

- To assess the pharmacokinetics (PK), biodistribution, and dosimetry of ⁶⁸Ga-PSMA-R2.
- To establish the optimal imaging method for determining location and burden of positive lesions on ⁶⁸Ga-PSMA-R2 positron emission tomography (PET) imaging in patients in comparison with lesions identified with conventional imaging scans (computed tomography (CT)/magnetic resonance imaging (MRI) and bone scan), and to calculate the agreement of ⁶⁸Ga-PSMA-R2 PET with conventional anatomical/functional imaging on a per patient basis.

3. EXPERIMENTAL DESIGN

3.1. Overall Study Design and Plan

This study is an open label, multi-center, single dose, safety and tolerability study of a diagnostic radio-pharmaceutical, in subjects with prostate cancer in biochemical relapse and metastatic prostate cancer (mPCa). During Phase 1, approximately 6 subjects will enter the trial unit on the morning of dosing and will remain there for approximately 6 hours post-injection in order to assess the pharmacokinetics (PK), biodistribution vs. time, and dosimetry for critical organs. Serial blood and urine samples will be collected for PK characterization.

Two groups of up to 12 subjects will be enrolled in the second Phase. One group will consist of subjects with prostate cancer in biochemical relapse (PC-BR), while the other will consist of patients with prostate cancer in the metastatic stage (MPs). If preliminary data analysis from the Phase-1 portion of the study returns sufficient data for dosimetry, all Phase-II subjects will have

PET-imaging reduced to 2 whole body scans within the optimal time frame, and blood and urine sampling will be omitted.

Subjects enrolled in the dosimetry set of Phase 1, will enter the trial unit on the morning of the exam. Patients will receive a single dose of 3 MBq/kg, (≥ 150 and ≤ 250 MBq), of ^{68}Ga -PSMA-R2. The product will be prepared prior to administration and injected intravenously and each patient will undergo a dosimetry study based on a series of PET/CT images.

3.2. Planned Pharmacokinetics Sampling Schedule

- Whole blood samples (1 mL in heparinized tubes) will be collected from each of 6 patients during Phase 1 immediately before administration of ^{68}Ga -PSMA-R2 from the opposite arm of drug injection and then at the following approximate time-points following injection: 5 min, 10 min, 20 min, 40 min, 1 h, 2 h, 4 h, and 6 h
- Total urine excreted from each of 6 patients during Phase 1 will be collected pre-injection and as follows post-injection: 0-20 min, 20 min – 1 h, 1 h – 2 h, 2 h -4 h and 4 h – 6 h.

4. GENERAL REPORTING SPECIFICATION:

4.1. Analyses to be Performed

Listings, tables, and graphs that summarize ^{68}Ga -PSMA-R2 whole blood concentrations and pharmacokinetic parameters (as applicable) and ^{68}Ga -PSMA-R2 urine recovery will be created by [REDACTED]. The data will be compiled into a final pharmacokinetic (PK) report.

4.2. Template and Guidelines to be Followed

Reporting methods generally follow FDA guidelines for clinical data analysis and reporting.

4.3. Statistical Methods Planned

No formal statistical analysis beyond descriptive statistics is planned. Descriptive statistics will include number of observations (N), mean, standard error, geometric mean, %CV geometric mean (coefficient of variation of the geometric mean) calculation, median, min, and max for each parameter, where appropriate.

Blood radioactivity data will be converted into mass concentration data (e.g. ng/mL), considering the specific radioactivity of the product and its radioactive decay. Individual whole blood concentrations will be sorted by dose and subject number and summarized with descriptive statistics using protocol-specified sampling times. Individual pharmacokinetic parameters will be listed by subject number and summarized with descriptive statistics. Both individual and geometric mean profiles of whole blood concentrations of ^{68}Ga -PSMA-R2 will be presented graphically using protocol-specified sampling times. For all analyses, actual blood sampling times will be used in the calculation of individual pharmacokinetic parameters.

Missing data will not be imputed except for:

- Tabulation of whole blood concentration data, where concentrations that are below the limit of quantification (BLQ) will be treated as zero.
- Calculation of PK parameters, where BLQ concentrations will be treated as zero.
- Embedded (i.e., BLQ concentrations bracketed by quantifiable data, in a series of concentration measurements constituting a reasonable profile) and/or terminal (after the last measurable concentration) BLQ concentrations will be treated as 'missing'.

Unscheduled measurements will be listed in the individual data listings. Unscheduled measurements will be excluded from the descriptive statistical analysis.

